5.2 Dose Modification of Study Drugs

5.2.1 Dose modification of SHR-1210

Dose increases and reductions of SHR-1210 are not permitted. If SHR-1210 treatment is interrupted due to a toxicity, the subject may resume the treatment at the original dose after the toxicity is resolved. AEs related to SHR-1210 may be immune toxicities, and may occur shortly after the first dose or several months after the last dose. If the conditions listed in [Table 7](#) occur, the use of SHR-1210 should be interrupted. During the study, the investigator must consult with the sponsor if the investigator considers that an adjustment listed in [Table 7](#) is inappropriate based on the benefit-to-risk ratio of subjects or that SHR-1210 treatment should be interrupted or resumed due to a condition not listed in the table.

Table 7. Dose modification criteria for SHR-1210 due to immune-related toxicity

SHR-1210-Related Toxicity	Grade for Interruption	Resumption	Discontinuation
Diarrhea/Colitis	Grade 2-3	Recovered to Grade 0-1	Toxicity has not resolved by 12 weeks after the last dose, or the corticosteroid dose cannot be reduced to prednisone 10 mg/day (or equivalent) or lower within 12 weeks after the last dose.
	Grade 4	Discontinuation	Discontinuation
AST/ALT or Bilirubin Increased	Grade 2	Recovered to Grade 0-1	Toxicity has not resolved by 12 weeks after the last dose, or the corticosteroid dose cannot be reduced to prednisone 10 mg/day (or equivalent) or lower within 12 weeks after the last dose.
	Grade 3-4	Discontinuation ^a	Discontinuation
Type 1 Diabetes Mellitus (new onset) or Hyperglycemia with Signs of β-cell Failure	Grade 3-4 or new-onset type 1 diabetes	SHR-1210 treatment may only be resumed after the clinical and metabolic conditions of the subject are stabilized.	
Hyperthyroidism	Grade 3	Toxicity reduced to Grade 0-1	Toxicity has not resolved by 12 weeks after the last dose, or the corticosteroid dose cannot be reduced to prednisone 10 mg/day (or equivalent) or lower within 12 weeks after the last dose.
	Grade 4	Discontinuation	Discontinuation
Hypothyroidism	Grade 2-4	Study treatment can be continued after starting thyroxine replacement therapy	

SHR-1210-Related Toxicity	Grade for Interruption	Resumption	Discontinuation
Pneumonia	Grade 2	Toxicity reduced to Grade 0-1	Toxicity has not resolved by 12 weeks after the last dose, or the corticosteroid dose cannot be reduced to prednisone 10 mg/day (or equivalent) or lower within 12 weeks after the last dose.

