	Grade 3-4	Discontinuation	Discontinuation
Immune-Related Hypophysitis	Grade 2-3	The SHR-1210 treatment may continue after the toxicity reduces to Grade 0-1 and the hormone replacement therapy starts.	Toxicity has not resolved by 12 weeks after the last dose, or the corticosteroid dose cannot be reduced to prednisone 10 mg/day (or equivalent) or lower within 12 weeks after the last dose.
	Grade 4	Discontinuation	Discontinuation
Renal Failure or Nephritis	Grade 2	Toxicity reduced to Grade 0-1	Toxicity has not resolved by 12 weeks after the last dose, or the corticosteroid dose cannot be reduced to prednisone 10 mg/day (or equivalent) or lower within 12 weeks after the last dose.
	Grade 3-4	Discontinuation	Discontinuation
Infusion reactions	Grade 2 ^b	Symptoms disappeared	Discontinue the drugs if the symptoms recur after adequate premedication.
	Grade 3-4	Discontinuation	Discontinuation
Other T-related toxicities ^c	Grade 3	Toxicity reduced to Grade 0-1	Toxicity has not resolved by 12 weeks after the last dose, or the corticosteroid dose cannot be reduced to prednisone 10 mg/day (or equivalent) or lower within 12 weeks after the last dose.
	Grade 4	Discontinuation	Discontinuation

Treatment should be discontinued if any grade ≥ 3 treatment-related AE recurs (grade ≥ 2 pneumonia) or any life-threatening event recurs.

- a) For subjects with liver metastasis and grade 2 AST or ALT increased at baseline, if the AST or ALT increased $\geq 50\%$ from baseline persists for at least 1 week, the treatment shall be discontinued.
- b) If the symptoms resolve within 1 hour after dechallenge, and the infusion can be resumed at 50% of the initial infusion rate. Otherwise, the treatment can only be resumed until symptoms are fully resolved. Premedication is required prior to the next dose. Refer to section 5.6.2 "Recommendations on infusion reaction management" for further management.

- c) For subjects with intolerable or persistent grade 2 treatment-related AEs, the investigator may consider interrupting SHR-1210 treatment if appropriate, and the treatment should be discontinued if toxicity fails to decrease to Grade 0-1 within 12 weeks after the last dose.

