7.2.7 Adverse Events of Special Interest

Special interest events include the following:

- Grade ≥ 3 infusion reactions;
- Grade ≥ 2 diarrhea/colitis, uveitis, and interstitial pneumonia;
- Grade ≥ 3 other immune-related AEs;
- Grade 4 amylase or lipase increased.

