7.4.4 Reporting of Special Interest Events

For SIEs specified in the study protocol, the investigator must complete the "Report of Special Interest Event for Hengrui Clinical Studies" and report to the sponsor within 24 hours of knowing of the event.

If the SIE is also an SAE, the "NMPA Serious Adverse Event Report Form" should also be completed and reported to the relevant authorities according to the SAE reporting procedure.

SIEs are shown in section [7.2.7](#).

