Grade 2 Diarrhea : Increase of 4-6 stools per day over baseline; intravenous infusion of < 24 h is required; daily living is not affected; Colitis : Abdominal pain; hematochezia.	
Delay the immunotherapy according to the study protocol;Symptomatic treatment.	
If it is improved to Grade 1:
 
Resume the immunotherapy according to the study protocol. 
If it lasts for > 5-7 days or relapses:
 
Intravenous administration of 0.5-1.0 mg/kg/d methylprednisolone or an equivalent orally administrated dose;When the symptoms improve to grade 1, reduce the dose of steroids for at least 1 month and consider prophylactic antibiotics to prevent opportunistic infections, then resume the immunotherapy as per study protocol. 
If the symptoms aggravated or persisted after > 3-5 days of oral administration of steroids:
 
Provide treatment according to the method for grade 3/4 situations.
Grade 3-4 Diarrhea (Grade 3) : Increase of ≥ 7 stools per day over baseline; fecal incontinence; intravenous infusion of ≥ 24 h is required; daily living is affected; Colitis (Grade 3) : Severe abdominal pain, indications for medical interventions, peritoneal signs; Grade 4 : Life-threatening, perforation	
Terminate the immunotherapy according to the study protocol;Intravenous administration of 1.0-2.0 mg/kg/d methylprednisolone or an equivalent dose via intravenous injection;Add prophylactic antibiotics to prevent opportunistic infections;Consider lower GI endoscopy.	
If symptoms improve:
 
Continue steroid treatment until the symptoms recover to grade 1, then gradually reduce the dose of steroids for at least 1 month. 
If it lasts for > 3-5 days or relapses after improvement:
 
Add 5 mg/kg infliximab (if there are no contraindications). Note: Do not use infliximab in the case of perforation/sepsis.

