Grade 2 AST/ALT > 3 × ULN, but ≤ 5 × ULN and/or TBIL > 1.5 × ULN but ≤ 3 × ULN	
Delay the immunotherapy according to the study protocol;Increase the monitoring frequency to once every 3 days.	
If symptoms recover to the baseline level:
 
Resume routine monitoring and resume the immunotherapy according to the study protocol. 
If elevation persists for > 5-7 days or aggravates:
 
Intravenous administration of 0.5-1 mg/kg/d methylprednisolone or an equivalent orally administrated dose. If LFT recovers to grade 1 or to the baseline level, reduce the dose of steroids for at least 1 month, and consider prophylactic antibiotics to prevent opportunistic infection and then resume the immunotherapy according to study protocol.
Grade 3-4 AST/ALT > 5 × ULN and/or TBIL > 3 × ULN	
Terminate the immunotherapy according to the study protocol*;Increase the monitoring frequency to once every 1-2 days;Intravenous administration of 1.0-2.0 mg/kg/d methylprednisolone or an equivalent dose via intravenous injection**;Add prophylactic antibiotics to prevent opportunistic infections;Consultation with the gastroenterology department.	
If it recovers to Grade 2:
 
Reduce the dose of steroids for at least 1 month. 
If not improving, or even aggravating or recurring after > 3-5 days:
 
Add mycophenolate mofetil 1 g bid;If the symptoms are not relieved within 3-5 days, other immunosuppressants are considered based on local guidelines.

Once a patient given intravenous injections of steroids shows a sustained clinical improvement, the patient can switch to an equivalent dose of oral corticosteroids (e.g., prednisone) by the time or before the dose of steroid injections starts to be gradually reduced. When switching to oral corticosteroids with an equivalent dose, it should be considered that the bioavailability of oral corticosteroids is relatively low.

* If AST/ALT ≤ 8 × ULN and TBIL ≤ 5 × ULN, the immunotherapy can be delayed rather than discontinued.

**For Grade 4 hepatitis, the recommended starting dose of methylprednisolone intravenous injection is 2 mg/kg/d.

4. Management Principles for Endocrine Adverse Events

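### Appendix 4 is out of line with Table 7 on SHR-1210 in two narrow cases: it permits delay for some Grade 3-4 liver events where Table 7 stops, and says terminate for a first Grade 3 colitis where Table 7 permits resumption

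*Protocol*

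**What the plan says.** **Table 7 (Protocol 5.2.1).** The diarrhea/colitis entry reads "Diarrhea/Colitis Grade 2-3 Recovered to Grade 0-1": interrupt at Grade 2-3, resume on recovery. The general rule above the table is permissive: "the subject may resume the treatment at the original dose after the toxicity is resolved". Grade 4 is discontinuation. SHR-1210 is also discontinued if the toxicity has not resolved, or steroids have not come down to prednisone 10 mg/day or less, within 12 weeks of the last dose, or if a Grade 3 or higher related event recurs.

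For raised AST/ALT or bilirubin, Grade 2 is interruption and Grade 3-4 is discontinuation. Footnote a covers patients with liver metastasis and Grade 2 AST/ALT at baseline: if a rise of at least 50% "from baseline persists for at least 1 week, the treatment shall be discontinued".

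**Appendix 4.** The diarrhea/colitis row groups Grade 3 with Grade 4 and says "Terminate the immunotherapy according to the study protocol". Its follow-up column covers steroids and infliximab but not resumption. The hepatic Grade 3-4 row (AST/ALT >5 x ULN and/or TBIL >3 x ULN) uses the same words with an asterisk. The asterisked note says that with AST/ALT at most 8 x ULN and TBIL at most 5 x ULN, "the immunotherapy can be delayed rather than discontinued".

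**Status of the two texts.** Appendix 4 introduces itself as reference material for all immuno-oncology drugs. Section 5.6.1 calls its content rules, and also says that procedures from similar drugs serve as references for the investigator. Section 5.2.1 states that "the investigator must consult with the sponsor if the investigator considers that an adjustment listed in" Table 7 is inappropriate on benefit-risk grounds. No sentence ranks the two.

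**The concern.** An investigator facing one of these events can find two protocol texts that point different ways on the same drug.

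The hepatic case matters more. A patient whom Table 7 takes off SHR-1210 could, under the Appendix 4 footnote, be held and remain a candidate for re-treatment. The Appendix 4 hepatic Grade 3-4 row gives no criterion for restarting, so the delay is open-ended.

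In the colitis case the risk runs the other way. A patient with a resolved first Grade 3 event, whom Table 7 would allow to resume, could be taken off the drug.

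Sites and monitors could also record the same decision differently, because SAP Section 8 lists not taking study drug according to the protocol as a deviation.

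**Working it through.** The plan states no figure to reproduce. The check sets the two texts side by side by toxicity and grade and finds where they part. It takes the grade boundaries from the Appendix 4 hepatic table: Grade 2 is AST/ALT >3 to 5 x ULN or TBIL >1.5 to 3 x ULN, and Grade 3-4 lies above that.

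| Situation | Table 7 | Appendix 4 | Agree? |
|---|---|---|---|
| AST/ALT >8 x ULN or TBIL >5 x ULN | Discontinue | Terminate (footnote does not apply) | Yes |
| AST/ALT >5 to 8 and/or TBIL >3 to 5 x ULN, neither above its ceiling | Discontinue | Delay permitted | **No** |
| Grade 4 diarrhea/colitis | Discontinue | Terminate | Yes |
| Recurrent Grade 3 diarrhea/colitis, or unresolved at 12 weeks | Discontinue | Terminate | Yes |
| First Grade 3 diarrhea/colitis, resolved within the limits | Interrupt, may resume at Grade 0-1 | Terminate, no resume step | **No** |
| Grade 2 diarrhea/colitis | Interrupt, may resume at Grade 0-1 | Delay, resume at Grade 1 | Yes |

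**Does Table 7 footnote a remove the hepatic conflict?** It does not.
- It applies only to liver metastasis with Grade 2 AST/ALT at baseline. For all other patients the plain Grade 3-4 rule stands.
- Within that subgroup, inclusion criterion 8f allows AST/ALT up to 5 x ULN. A 50% rise from the highest eligible value gives 1.5 x 5 = 7.5 x ULN. This is above 5, so it falls in the Appendix 4 Grade 3-4 row, and below 8, so the delay footnote still applies.
- If that rise has lasted at least 1 week and TBIL is at most 5 x ULN, Table 7 discontinues and Appendix 4 permits delay. A smaller or shorter rise does not trigger footnote a, and there is then no conflict. This shows only that the overlap exists, not how often it occurs.

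**Is the colitis difference deliberate?** The wording of Appendix 4 leaves that open. Its Grade 2 diarrhea/colitis row has a resume step, and its Grade 3-4 skin row offers delay or discontinuation, also with a resume step. The Grade 3-4 diarrhea/colitis row has neither, which suggests a real stop. Against that, the row refers back to the study protocol, which can be read as deferring to Table 7.

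**The case against.** The strongest reply is that precedence is already supplied in substance. Section 5.2.1 holds the dosing rules for SHR-1210 and sets one route for departing from them, through the sponsor. Appendix 4 is generic reference text. The colitis row and the asterisked hepatic row both refer back to the protocol. Other controls exist: Grade 2 or higher "diarrhea/colitis, uveitis, and interstitial pneumonia", and other Grade 3 or higher immune-related events, are special interest events that the investigator must "report to the sponsor within 24 hours of knowing of the event".

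Much of this stands, and it rules out a stronger reading. A reader might infer that the protocol issues flatly opposite commands, so that any action breaches one text. It does not. Table 7 only permits resumption after colitis, the hepatic footnote only permits delay, and Section 4.5.2 lets the investigator stop for other reasons. Stopping SHR-1210 satisfies both texts in both cases. Nor are the texts of equal standing: the signs favour Table 7.

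The reply does not remove the hepatic point. The footnote hangs on a row that defers to the protocol, but it reads as an exception to that row and has no deferring words of its own. An investigator who relies on it as protocol text may not think that Table 7 is being departed from, so the duty to consult may not come to mind. The 24-hour report tells the sponsor that the event happened; it does not say which dosing rule applies.

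**Conclusion.** Wrong as written, of minor severity: an internal inconsistency between a dosing table and a reference appendix.

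The hepatic footnote is the main point, because it permits what Table 7 rules out and does so in the less cautious direction. It is confined to AST/ALT >5 to 8 x ULN and/or TBIL >3 to 5 x ULN with neither above its ceiling. In the footnote a subgroup it is confined to a rise of at least 50% that has lasted at least 1 week with values still within those ceilings. The colitis row is the softer point, confined to a first Grade 3 event that resolves within the Table 7 limits.

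The documents give no frequency for either overlap. Protocol 1.3.1 reports treatment-related AST increase in 8.2%, ALT increase in 6.7% and bilirubin increase in 5.9% of 539 patients. These are not broken down by grade, so they do not size the overlap.

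A reader might also infer a threat to the primary result. The documents do not support that: the ORR definition, the full analysis set and the stage thresholds do not depend on which text is followed.

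The conclusion assumes that Table 7 and Appendix 4 use the same CTCAE grade boundaries.

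**What to change.** 1. Delete the hepatic delay footnote in Appendix 4, or make it expressly subject to Table 7 and its footnote a.
2. Split the Appendix 4 Grade 3-4 diarrhea/colitis row to match Table 7: delay at Grade 3, with resumption under the Table 7 conditions, and terminate at Grade 4.
3. Add one sentence, in 5.2.1 or at the head of Appendix 4: where the two differ on SHR-1210 for the same toxicity and grade, Table 7 governs.

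Appendix 4 should not be cut back to supportive care only. It contains cautious steps that Table 7 does not list as such: considering delay for Grade 1 pneumonitis, delay for persistent or recurrent Grade 1-2 rash, and termination for suspected adrenal crisis. Limiting the precedence sentence to the same toxicity and grade keeps these in force.

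The cost is a protocol wording amendment with the usual ethics review. Sample size, analysis and data collection do not change.

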Appendix 4 Management Principles for Immune Related Adverse Events

The principles specified in this section can be used as reference for the investigator when managing immune-related AEs. The principles can be added after discussion with the representatives of the sponsor. The principles are applicable to all immuno-oncology drugs and regimens.

The general principle is that AEs should be carefully evaluated and the differential diagnosis be made in accordance with the standard medical practice. Non-inflammatory causes should be considered and properly handled.

Corticosteroids are preferable drug for immuno-oncology treatment-related AEs. An oral dose equivalent to the recommended IV dose can be considered for ambulatory patients with low grade toxicity. The low bioavailability of oral administration should be taken into account when switching to the equivalent dose of oral corticosteroids.

Consultation with an internist or surgeon is recommended, especially before an invasive diagnostic or therapeutic procedure.

The frequency and severity of related adverse events included in these protocols will depend on the cancer immunotherapy or regimen being used.

1. Management Principles for Gastrointestinal Adverse Events

Inflammatory causes of disease should be excluded. Opioids/anesthetics may mask the symptoms of perforation. Do not use infliximab in the case of perforation/sepsis.

Diarrhea/Colorectitis Grade (NCI CTCAE v4)	Handling	Follow-Up
Grade 1 Diarrhea : Increase of < 4 stools per day over baseline; Colitis : No symptom.	
Continue the immunotherapy according to the study protocol;Symptomatic treatment.	
Closely monitor aggravated symptoms.Educate subjects to report aggravated symptoms immediately. 
If it is aggravated:
 
Provide treatment according to the method for grade 2 or grade 3/4 situations.

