Once a patient given intravenous injections of steroids shows a sustained clinical improvement, the patient can switch to an equivalent dose of oral corticosteroids (e.g., prednisone) by the time or before the dose of steroid injections starts to be gradually reduced. When switching to oral corticosteroids with an equivalent dose, it should be considered that the bioavailability of oral corticosteroids is relatively low.

2. Management Principles for Pulmonary AEs

Inflammatory causes of disease should be excluded. If it is due to a non-inflammatory cause, a symptomatic treatment should be given while the immunotherapy should be continued. Imaging evaluation and consultations with the respiratory department should be performed.

Grade of Pneumonitis (NCI CTCAE v4)	Handling	Follow-Up
Grade 1 Only radiographic changes	
Consider delaying the immunotherapy;Monitor symptoms every 2-3 days;Consider consulting with respirologist and infectious diseases specialist.	
Repeat imaging examinations at least every 3 weeks. 
If it is aggravated:
 
Provide treatment according to the method for grade 2 or grade 3/4 situations.
Grade 2 Mild to moderate new symptoms	
Delay the immunotherapy according to the study protocol;Consult with respirologist and infectious diseases specialist;Intravenous administration of 1.0 mg/kg/d methylprednisolone or an equivalent orally administrated dose;Consider bronchoscopy and lung biopsy.	
Repeat imaging examinations every 1-3 days. 
If symptoms improve:
 
When symptoms return to near baseline levels, reduce the dose of steroids for at least 1 month and then resume the immunotherapy as per study protocol while considering prophylactic antibiotics. 
If the symptoms are not improved or aggravated after 2 weeks:
 
Provide treatment according to the method for grade 3/4 situations.

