Grade 3-4 Severe new symptoms; new onset/aggravation of hypoxia; life-threatening.	
Terminate the immunotherapy according to the study protocol;Consult with respirologist and infectious diseases specialist;Intravenous administration of 2-4 mg/kg/d methylprednisolone or an equivalent dose via intravenous injection;Add prophylactic antibiotics to prevent opportunistic infections;Consider bronchoscopy and lung biopsy.	
If symptoms improve to the baseline level:
 
Gradually reduce the dose of steroids for at least 6 weeks. 
If the symptoms are not improved or aggravated after 48 h:
 
Add other immunosuppressants (e.g., infliximab, cyclophosphamide, intravenous immunoglobulin or mycophenolate mofetil).

Once a patient given intravenous injections of steroids shows a sustained clinical improvement, the patient can switch to an equivalent dose of oral corticosteroids (e.g., prednisone) by the time or before the dose of steroid injections starts to be gradually reduced. When switching to oral corticosteroids with an equivalent dose, it should be considered that the bioavailability of oral corticosteroids is relatively low.

3. Management Principles for Hepatic Adverse Events

Non-inflammatory causes of disease should be excluded. If it is due to a non-inflammatory cause, a symptomatic treatment should be given while the immunotherapy should be continued. Consider imaging examinations to rule out obstruction/tumor progression.

Elevation Grade in the Hepatic Function Test (NCI CTCAE v4)	Handling	Follow-Up
Grade 1 AST/ALT > 3 × ULN and/or TBIL > 1 × ULN but ≤ 1.5 × ULN	
Continue the immunotherapy according to the study protocol.	
Continue hepatic function monitoring as per study protocol. 
If it is aggravated:
 
Provide treatment according to the method for grade 2 or grade 3/4 situations.

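### Protocol Appendix 4, hepatic table: the Grade 1 AST/ALT range has no upper bound and overlaps Grades 2 to 4, and the rows and their footnote need reconciling with Table 7

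*Protocol*

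**What the plan says.** Protocol Appendix 4, section 3 (hepatic), sets out three rows under an NCI CTCAE v4 heading:

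- Grade 1: "AST/ALT > 3 × ULN and/or TBIL > 1 × ULN but ≤ 1.5 × ULN". Action: "Continue the immunotherapy according to the study protocol".
- Grade 2: "AST/ALT > 3 × ULN, but ≤ 5 × ULN and/or TBIL > 1.5 × ULN but ≤ 3 × ULN". Action: "Delay the immunotherapy according to the study protocol", with monitoring every 3 days.
- Grade 3-4: "AST/ALT > 5 × ULN and/or TBIL > 3 × ULN". Action: "Terminate the immunotherapy according to the study protocol". A footnote to this action allows delay instead of discontinuation when AST/ALT is at most 8 × ULN and TBIL at most 5 × ULN.

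Protocol section 5.2.1, Table 7, acts by grade for AST/ALT or bilirubin increase. Grade 2 is interruption, with resumption on recovery to Grade 0-1, and Grade 3-4 is discontinuation. Section 7.3.1 grades severity by NCI-CTCAE v4.03. Section 5.6.1 refers investigators to Appendix 4 for the safety management rules, and Appendix 4 describes itself as reference material.

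On causes, the gastrointestinal and pulmonary sections of Appendix 4 open with "Inflammatory causes of disease should be excluded". The hepatic and endocrine sections open with the same sentence about non-inflammatory causes. The general principle at the head of the appendix says "Non-inflammatory causes should be considered and properly handled".

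**The concern.** A toxicity table should assign a laboratory value to one row. Here an AST or ALT of 4 × ULN fits a row that continues immunotherapy and a row that delays it. The position matters because this table is where the protocol attaches ULN multiples to AST/ALT grades: Table 7 says what to do at Grade 2 or Grade 3-4 but not where those grades begin. A site that follows section 5.6.1 to find the cut-offs arrives at the overlapping rows.

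Two features add to it. Grade 1 is used as a recovery level as well as a starting level, so an unbounded Grade 1 blurs when a subject has recovered. Also, subjects with liver metastasis may enrol with AST and ALT up to 5 × ULN (section 4.1, criterion 8f), so some could enter the trial already inside the overlap.

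The stake is consistent handling of liver events. SAP section 11.4.1 counts treatment-emergent events that lead to interruption or discontinuation, and those counts depend on which action a site takes.

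**Working it through.** No sample size, power or error rate is involved, so the check sets the rows side by side. All values are multiples of ULN.

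| Appendix 4 row | AST/ALT | TBIL | Action |
|---|---|---|---|
| Grade 1 | above 3, no upper limit | above 1 to 1.5 | continue |
| Grade 2 | above 3 to 5 | above 1.5 to 3 | delay |
| Grade 3-4 | above 5 | above 3 | terminate (footnote: delay possible) |

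**1. Which term carries the Grade 1 upper limit.** The limit of 1.5 follows the TBIL term. If it applied to AST/ALT as well, the cell would require AST/ALT above 3 and at most 1.5, which no value satisfies. So the AST/ALT term has no upper limit.

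**2. Overlaps and gap in AST/ALT.**

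- Grade 1 and Grade 2: (3, ∞) ∩ (3, 5] = (3, 5]. All of Grade 2 lies inside Grade 1. Example: 4 × ULN meets both continue and delay.
- Grade 1 and Grade 3-4: (3, ∞) ∩ (5, ∞) = (5, ∞). Example: 6 × ULN meets both continue and terminate.
- Values in (1, 3] are in no row on the transaminase criterion.

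**3. Bilirubin.** The bands (1, 1.5], (1.5, 3] and (3, ∞) are consecutive and do not overlap. The overlap is confined to AST/ALT.

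**4. Recovery.** In the Grade 2 row, the steroid reduction and later resumption are tied to liver tests returning to Grade 1 or baseline. Table 7 resumes SHR-1210 at Grade 0-1. Under the literal Appendix 4 definition, a subject still at 4 × ULN already counts as Grade 1.

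**5. Footnote against Table 7.** Within the Appendix 4 Grade 3-4 row, the footnote permits delay in two regions:

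- AST/ALT above 5 to 8, with TBIL at most 5;
- TBIL above 3 to 5, with AST/ALT at most 8.

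Table 7 lists discontinuation for Grade 3-4. Its note a adds a separate criterion for subjects with liver metastasis and Grade 2 AST or ALT elevation at baseline, and contains no counterpart to the 8 and 5 × ULN limits. This comparison assumes that Grade 3-4 in Table 7 begins where Appendix 4 places it, since Table 7 gives no cut-offs of its own.

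**6. Causes to exclude.** Two organ sections say inflammatory (gastrointestinal, pulmonary) and two say non-inflammatory (hepatic, endocrine). The general principle sides with the latter. The skin section opens with a figure that is not reproduced, so its wording cannot be checked.

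**The case against.** The strongest reply is that the operative rule lies elsewhere. Appendix 4 is offered as reference, and each of its actions defers to the study protocol. SHR-1210 dosing is set by Table 7, and an investigator who thinks a Table 7 adjustment inappropriate must consult the sponsor. Grading by NCI-CTCAE v4.03 and then applying Table 7 gives one action. That stands. A reader might infer from the rows that the protocol gives two binding and incompatible dosing instructions for the same value; the documents do not support that.

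Secondly, the Grade 1 entry looks like a slip in one symbol. Every other band in the table runs in sequence, and nobody reading an ascending scale would place 6 × ULN in Grade 1. A translation or PDF-reading error in that cell cannot be excluded from the extracted text, although the bilirubin limits beside it came through intact. This makes the literal overlap less likely to be acted on. It does not touch the footnote mismatch.

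Thirdly, a reader might take the treatment-related AST and ALT increases in section 1.3.1 (8.2% and 6.7% of 539 subjects) as the size of the problem. They are not: they have no grade breakdown and come from subjects given SHR-1210 alone or in combination.

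Fourthly, the wording on causes has little consequence. The pulmonary paragraph can be read coherently by itself, so it is not self-contradictory. The differing sentences are an inconsistency between sections, and the intent can be recovered from the general principle and the follow-on text.

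**Conclusion.** The point holds as an internal inconsistency in a toxicity-management table, and it should be corrected. Read literally, AST/ALT Grade 1 covers the whole of Grade 2 and the whole AST/ALT range of Grade 3-4, and leaves values above ULN up to 3 × ULN without a row. Separately, the footnote and Table 7 differ on delay against discontinuation within Grade 3-4.

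The practical effect is limited by Table 7 and CTCAE v4.03 grading. It is not removed, because Table 7 prints no ULN cut-offs, section 5.6.1 sends investigators to the appendix, and Grade 1 also serves as a recovery level. How many subjects would fall in the overlap cannot be derived from the documents, and nothing in them shows that sites did act differently. ORR, sample size and error rates are unaffected.

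The conclusion on the rows rests on the Grade 1 cell being extracted correctly, which should be checked against the source protocol. The conclusion on the footnote does not depend on that cell, but rests on the cut-off assumption stated with that comparison.

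**What to change.** Reconcile the Appendix 4 hepatic rows and their footnote with each other, with Table 7 (including its note a) and with the CTCAE version named in the protocol, so that every AST/ALT value maps to one grade and one action, both at onset and at recovery. State which text prevails if Appendix 4 and Table 7 differ. The thresholds and the clinical rule are for the sponsor to decide; this review does not propose them.

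In the same edit, make the sentences on which causes to exclude consistent across the organ sections and with the general principle, and check the skin section against its figure.

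The cost is a wording change to one appendix and, if needed, a cross-reference or note in Table 7, submitted as a protocol amendment. No data collection, sample size or analysis changes.
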